4.1 Inclusion and Exclusion Criteria

4.1.1 Inclusion Criteria

- 101 Subject has provided written informed consent
- 102 Male or female ≥ 18 years of age at signing of informed consent
- 103 Known HIV infection with stable HIV therapy for ≥ 6 months prior to randomization and not expected to change during the duration of study participation. Stable HIV therapy is defined as no new agents added and no dose change of any HIV drug within 6 months prior to randomization
- 104 Cluster of differentiation 4 (CD4) ≥ 250 cells/mm³ for ≥ 6 months prior to randomization
- 105 HIV viral load ≤ 50 copies/mL at screening and ≤ 200 copies/mL for ≥ 6 months prior to randomization
- Subject on stable lipid-lowering therapy for ≥ 4 weeks prior to randomization and not expected to change during the duration of study participation. Subjects should be on maximally tolerated dose of statins. For some subjects, "maximally tolerated" may indicate no statin at all due to statin intolerance or contraindication to statin therapy. Statin intolerance or contraindication must be documented. A subject with statin intolerance must be evidenced by the following:
 - a. Must have tried at least 2 statins with failure to at least 1 of the statins at an average daily dose at or below the following doses due to intolerable myopathy (ie, myalgia [muscle pain, ache, or weakness without creatine kinase elevation]), myositis (muscle symptoms with increased creatine kinase levels), or rhabdomyolysis (muscle symptoms with marked creatine elevation, as defined under "b"):

atorvastatin: 10 mg

simvastatin: 10 mg

pravastatin: 40 mg

rosuvastatin: 5 mg

lovastatin: 20 mg

fluvastatin: 40 mg

pitavastatin: 2 mg

AND

Symptoms resolved or improved when statin dose was decreased or discontinued

For subjects that developed rhabdomyolysis, defined as creatine kinase > 10 × upper limit of normal (ULN), failure of only 1 statin at any dose is acceptable.

- Subject without known clinical atherosclerotic CVD (ASCVD): fasting LDL-C of ≥ 100 mg/dL (2.6 mmol/L) or non-HDL-C of ≥ 130 mg/dL (3.4 mmol/L) as determined by the central laboratory at screening. Subject with known clinical ASCVD: fasting LDL-C of ≥ 70 mg/dL (1.8 mmol/L) or non-HDL-C of ≥ 100mg/dL (2.6 mmol/L) as determined by the central laboratory. Clinical ASCVD is defined as a history of myocardial infarction, stable or unstable angina, coronary or other arterial revascularization, stroke, transient ischemic attack, or peripheral arterial disease presumed to be of atherosclerotic origin.
- 108 Fasting triglycerides ≤ 600 mg/dL (6.8 mmol/L) as determined by central laboratory during screening
- 109 Subject tolerates screening placebo injection

4.1.2 Exclusion Criteria

- Subject taking a combination of background lipid-lowering therapy and HIV therapy known to have significant drug-drug interaction as per Table 2
- New York Heart Association III or IV heart failure, or last known left ventricular ejection fraction < 30%
- Known opportunistic infection/AIDS defining illness (including but not limited to candidiasis of bronchi, trachea, esophagus, or lungs, invasive cervical cancer, coccidioidomycosis, cryptococcosis, chronic intestinal (> 1-month duration) cryptosporidiosis, cytomegalovirus disease (particularly cytomegalovirus [CMV] retinitis), HIV-related encephalopathy, herpes simplex: chronic ulcer(s) (> 28 days duration); or bronchitis, pneumonitis, or esophagitis, histoplasmosis, chronic intestinal (> 28 days duration) isosporiasis, Kaposi's sarcoma, lymphoma, mycobacterium avium complex, tuberculosis, pneumocystis carinii pneumonia, recurrent pneumonia, progressive multifocal leukoencephalopathy, salmonella septicemia, toxoplasmosis of brain, or wasting syndrome due to HIV within 1 year prior to randomization
- 204 Myocardial infarction, unstable angina, percutaneous coronary intervention, coronary artery bypass graft or stroke within 3 months prior to randomization
- Type 1 diabetes, new-onset (hemoglobin A1c [HbA1c] ≥ 6.5% or fasting plasma glucose ≥ 126 mg/dL at screening without known diagnosis) or poorly controlled (HbA1c ≥ 10%) type 2 diabetes by central laboratory during screening
- 206 Uncontrolled hypertension defined as sitting systolic blood pressure > 180 mmHg or diastolic blood pressure > 110 mmHg during screening
- Subject has taken a cholesterylester transfer protein inhibitor in the last 12 months prior to randomization
- 208 Moderate to severe renal dysfunction, defined as an estimated glomerular filtration rate < 30 mL/min/1.73 m² during screening

Date: 30 January 2017 Page 21 of 73

209 Persistent active liver disease or hepatic dysfunction defined as Child-Pugh score of C. Stable (in the opinion of the primary investigator and with aspartate aminotransferase [AST] and alanine aminotransferase [ALT] < 5 times ULN and not expected to require new treatment[s] during study) chronic hepatitis C of at least 1 year duration prior to randomization is allowed

210 Female subject of childbearing potential not willing to use acceptable method(s) of effective birth control during treatment with IP and for an additional 15 weeks after the end of treatment with IP. Female subjects of non-childbearing potential are not required to use contraception during the study and include those who have had a hysterectomy, bilateral salpingectomy, bilateral oophorectomy, or who are postmenopausal.

Postmenopausal is defined as 12 months of spontaneous and continuous amenorrhea in a female ≥ 55 years old; or age < 55 years but no spontaneous menses for at least 2 years; or age < 55 years and spontaneous menses within the past 1 year, but currently amenorrheic (eg, spontaneous or secondary to hysterectomy) and with postmenopausal gonadotropin levels (luteinizing hormone and follicle stimulating hormone levels > 40 IU/L) or postmenopausal estradiol levels (< 5 ng/dL) or according to the definition of "postmenopausal range" for the laboratory involved

Acceptable methods of effective birth control include:

- true sexual abstinence (when this is in line with the preferred and usual lifestyle of the subject. Periodic abstinence [eg, calendar, ovulation, symptothermal, postovulation methods], declaration of abstinence for the duration of a trial, and withdrawal are not acceptable methods of contraception]),
- surgical contraceptive methods (vasectomy or bilateral tubal ligation/occlusion),
- use of hormonal birth control methods (oral, intravaginal, transdermal, injectable, or implantable),
- intrauterine devices.
- intrauterine hormonal releasing system, or
- 2 barrier methods (each partner must use 1 barrier method) and at least 1 of barrier methods must include spermicide (males must use a condom: females must choose either a diaphragm OR cervical cap OR contraceptive sponge). If spermicide is not available in the country or region, the 2-barrier method without spermicide is acceptable.

Note: Additional medications given during treatment with evolocumab may alter the contraceptive requirements. These additional medications may require an increase in the number of contraceptive methods, the change in type of contraceptive methods and/or length of time that contraception is to be utilized or length of time breastfeeding is to be avoided. The investigator is to discuss these contraceptive changes with the study subject.

211 Female subject is pregnant or breast feeding, planning to become pregnant or planning to breastfeed during treatment with IP and/or within 15 weeks after the end of treatment with IP

Page 22 of 73

- 212 Malignancy (except non-melanoma skin cancers, cervical in-situ carcinoma, breast ductal carcinoma in situ, or stage 1 prostate carcinoma) within the last 5 years prior to randomization
- 213 Subject has previously received evolocumab or any other therapy to inhibit PCSK9
- Currently receiving treatment in another investigational device or drug study, or < 30 days before randomization since ending treatment on another investigational device or drug study(s) or planning to receive other investigational procedures while participating in this study
- Subject has known sensitivity to any of the active substances or their excipients to be administered during dosing, eg, carboxymethylcellulose
- Subject likely to not be available to complete all protocol-required study visits or procedures, and/or to comply with all required study procedures to the best of the subject's and investigator's knowledge
- 217 History or evidence of any other clinically significant disorder, condition or disease (with the exception of those outlined above) that, in the opinion of the investigator or Amgen physician, if consulted, would pose a risk to subject safety or interfere with the study evaluation, procedures, or completion

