6.8 Excluded Treatments, Medical Devices, and/or Procedures During Study Period

The following treatments are not permitted during the study:

any investigational therapies other than study-provided IP

The following treatments are not permitted during the blinded portion of the study:

 any lipid-lowering therapies not taken at the time of screening and enrollment (unless required in response to HIV worsening; see Section 9.1.2.1).

Product: Evolocumab
Protocol Number: 20130286
Date: 30 January 2017
Page 30 of 73

Please contact the Amgen medical monitor or designee if any of these therapies should be initiated during the blinded portion of the study. Note that a change in lipid-lowering therapy does not necessarily require ending IP administration.

During the open-label period, adjustments to background lipid-lowering therapy due to results of the unblinded lipid panel (ie, asymptomatic LDL-C) will not be allowed. Changes to background lipid-lowering therapy for other reasons such as adverse events are allowed during the open-label period.

The following treatments are not recommended in subjects treated with statins metabolized by cytochrome P450 (CYP) 3A4 (eg, simvastatin or atorvastatin) because of their potential impact on metabolism of certain statins:

medications or foods that are known potent inhibitors of CYP3A (eg, itraconazole, ketoconazole, and other antifungal azoles, macrolide antibiotics erythromycin, clarithromycin, and the ketolide antibiotic telithromycin, HIV or hepatitis C virus (HCV) PI, antidepressant nefazodone and grapefruit juice in large quantities (> 1 quart daily [approximately 1 Liter]) should not be used during the study. See Table 2 for additional details.

Protocol Number: 20130286 Date: 30 January 2017 Page 31 of 73

Table 2. Statin Interactions

Statin	Failure to Adjust Dosage for Concomitant Medications	Use with Contraindicated Medication (Risk X)
Atorvastatin	Atorvastatin > 40 mg while taking boceprevir, simeprevir, or nelfinavir; atorvastatin > 20 mg while taking clarithromycin, telithromycin, itraconazole, fosamprenavir, or ritonavir-boosted darunavir, fosamprenavir, or saquinavir	Concomitant use of atorvastatin with gemfibrozil, posaconazole, telaprevir, or tipranavir
Fluvastatin	Fluvastatin > 20 mg BID while taking fluconazole	Concomitant use of fluvastatin with gemfibrozil

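### A subject already taking a statin with gemfibrozil is eligible as worded and continues on both, although Table 2 lists that pair as contraindicated for all 7 statins

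*Protocol*

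**What the plan says.** Three parts of the protocol bear on background drug interactions at entry and on study.

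- **Entry.** The first exclusion in Protocol 4.1.2 removes a "Subject taking a combination of background lipid-lowering therapy and HIV therapy known to have significant drug-drug interaction as per Table 2". It is the only entry criterion that uses Table 2. Inclusion criterion 106 asks for stable lipid-lowering therapy for at least 4 weeks and a maximally tolerated statin. It names no lipid-lowering drug as unacceptable.
- **Table 2 (in Protocol 6.8).** Each statin has a dose-limit column and a contraindicated column. The contraindicated column reads, for example, "Concomitant use of atorvastatin with gemfibrozil, posaconazole, telaprevir, or tipranavir" and "Concomitant use of fluvastatin with gemfibrozil".
- **On study.** During the blinded portion, Protocol 6.8 does not permit "any lipid-lowering therapies not taken at the time of screening and enrollment", with an exception for HIV worsening. A separate item on potent CYP3A inhibitors does not name gemfibrozil. Protocol 3.1 continues the HIV and lipid-lowering drugs taken at randomization for the whole study, and 6.4 treats them as protocol-required therapy.

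**The concern.** The exclusion points to Table 2 as its source of unacceptable combinations but takes in only part of the table: pairs of a lipid-lowering drug with an HIV drug. The one drug that the table contraindicates with every statin is not an HIV drug. A site that applies the criterion word for word would pass a subject on a statin plus gemfibrozil. Section 3.1 would then keep both drugs in place for up to 52 weeks.

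What is at stake is subject safety and the agreement of the protocol with its own table. The contraindication comes from Table 2 itself, so the point needs no outside labelling.

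**Working it through.** There is no stated figure to reproduce and no power or alpha calculation applies. The check is a count and a comparison of rules.

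**Step 1. Count the Table 2 rows with gemfibrozil in the contraindicated column.**

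| Statin | Gemfibrozil contraindicated | Other contraindicated drugs in the row |
|---|---|---|
| Atorvastatin | yes | yes |
| Fluvastatin | yes | none |
| Lovastatin | yes | yes |
| Pitavastatin | yes | none |
| Pravastatin | yes | none |
| Rosuvastatin | yes | none |
| Simvastatin | yes | yes |

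The count is 7 of 7. In 4 of the 7 rows gemfibrozil is the only entry in that column.

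**Step 2. Test a statin-gemfibrozil pair, in use at entry, against each rule that might catch it.**

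- Exclusion citing Table 2: needs an HIV drug as one member of the pair. Not met.
- Inclusion criterion 106: the pair can be stable lipid-lowering therapy. Met, so the subject passes.
- Exclusion 217: concerns a disorder, condition or disease, not a drug pair. Not met.
- 6.8, blinded-period lipid rule: reaches only drugs not taken at entry. Not met.
- 6.8, CYP3A item: gemfibrozil is not listed. Not met.
- 6.5: limits what the investigator may prescribe during the study. It is not an entry rule.

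Entry criteria that capture the pair: 0.

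**Step 3. Check whether other contraindicated drugs are missed in the same way.** The HIV drugs in the column fall under the exclusion, as does cobicistat if it is counted as part of the HIV regimen. The azoles, macrolides, telithromycin, HCV protease inhibitors and nefazodone are covered by the CYP3A item in 6.8. Gemfibrozil is reached by neither, which suggests an oversight.

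**Step 4. Size the group in which the pair could occur.** Protocol 3.1 plans about 450 subjects, with about 10% and at most 20% not on a statin. Expected statin users: 450 × (1 − 0.10) = 405. If the 20% limit is reached: 450 × (1 − 0.20) = 360. How many of these would also take gemfibrozil is not given and cannot be derived.

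**The case against.** The case against has several sound parts.

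- **New gemfibrozil is already barred in the blinded period.** This is correct, apart from the HIV-worsening exception. A reader might infer that gemfibrozil is uncontrolled altogether, and the documents do not support that. The gap is limited to pairs in use at entry.
- **Table 2 sits inside the section on excluded treatments, and 6.5 withholds what 6.8 lists.** A careful site that opens Table 2 would see gemfibrozil in every row. One could also stretch the exclusion to mean the subject's whole regimen, since every subject is on HIV therapy. Neither reading is stated, and 6.5 governs new prescribing.
- **Nothing forbids stopping gemfibrozil.** Section 8.2 lets the investigator or sponsor withdraw protocol-required therapies, and the hepatotoxicity rules in 6.3 can stop them. CK, ALT and AST are measured at screening, day 1 and weeks 12, 24, 36 and 52, and SAP 10.6.2 summarizes CK above 5 and 10 times the upper limit of normal. These measures lower the risk but act after entry.
- **Further detail may be in the product instruction manual** that 6.4 mentions. It is not available here.

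A reader might also infer a second conflict: that 6.8 forbids HIV protease inhibitors that Table 2 accepts with atorvastatin, leaving an eligible subject no compliant course. The class is indeed named ("HIV or hepatitis C virus (HCV) PI, antidepressant nefazodone and grapefruit juice in large quantities") and the item says such drugs "should not be used during the study. See Table 2 for additional details". But its lead-in is advisory ("The following treatments are not recommended in subjects treated with statins metabolized by cytochrome P450 (CYP) 3A4 (eg, simvastatin or atorvastatin"), and the item defers to Table 2, which sets dose limits such as "atorvastatin > 20 mg while taking clarithromycin, telithromycin, itraconazole, fosamprenavir, or ritonavir-boosted darunavir, fosamprenavir, or saquinavir". Sections 3.1 and 6.4 and the protease-inhibitor subgroup in SAP 7.4 show that continuation is intended. Keeping both drugs within the limit departs only from a recommendation, and criteria 103 and 106 are entry criteria about what is expected. This is at most a wording clarification.

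**Conclusion.** The concern holds for one situation: a statin with gemfibrozil already in use at entry. Table 2 contraindicates the pair for 7 of 7 statins, no entry criterion captures it, and 3.1 has it continue. The safeguards elsewhere in the protocol reduce the consequence without closing the gap.

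The weight is modest. The trial does not start the pair, and the number of subjects affected is unknown. The primary comparison, alpha and power are unaffected.

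The conclusion rests on reading the exclusion as written, and on taking gemfibrozil to be a lipid-lowering drug and not an HIV drug. The documents do not classify it. The second part of that assumption places it outside the exclusion; the first brings new use under the blinded-period ban.

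**What to change.** In the exclusion, directly after the reference to Table 2, add: *, or taking a statin together with gemfibrozil or any other drug listed as contraindicated for that same statin in Table 2*.

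The words *that same statin* matter. A clause covering any drug in the contraindicated column would also exclude, for example, pravastatin with an HIV protease inhibitor, because that class appears in the lovastatin and simvastatin rows.

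The cost is one clause by amendment. A few subjects on such pairs become ineligible until the pair is stopped; they could then be rescreened under 7.2.2 after the 4 stable weeks that criterion 106 requires. Eligibility changes only for pairs that the protocol already calls contraindicated. Sample size, randomization and analysis stay as they are.

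Optionally, the same amendment could say in 6.8 that the Table 2 dose limits govern HIV protease inhibitors taken with atorvastatin.

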5. SUBJECT ENROLLMENT

Before subjects begin participation in any study-specific activities/procedures, Amgen requires a copy of the site's written institutional review board/independent ethics committee (IRB/IEC) approval of the protocol, informed consent form (ICF), and all other subject information and/or recruitment material, if applicable (see Section 11.2). All subjects must personally sign and date the ICF before commencement of study specific activities/procedures.

A subject is considered enrolled upon randomization. The investigator is to document this decision and date, in the subject's medical record and in the enrollment case report form (CRF).

Each subject who enters into the screening period for the study (defined as the point at which the subject signs the ICF) receives a unique subject identification number before any study-related activities/procedures are performed. The subject identification number will be assigned **via** IVRS/IWRS. This number will be used to identify the subject throughout the clinical study and must be used on all study documentation related to that subject.

Subjects who are unable to complete or meet eligibility on initial screening will be permitted to re-screen, except for subjects **who do not meet inclusion criterion 107** (see Section 7.2.2).

Protocol Number: 20130286 Page 23 of 73

Product: Evolocumab Date: 30 January 2017

The subject identification number must remain constant throughout the entire clinical study; it must not be changed after initial assignment, including if a subject is rescreened. This number will not necessarily be the same as the randomization number assigned for the study.

5.1 **Randomization/Treatment Assignment**

Subjects who tolerate the placebo injection, complete all screening procedures, and successfully meet all eligibility criteria at the end of screening will be randomized via IVRS/IWRS and will return to the study site for day 1 procedures while continuing their background HIV and lipid-lowering treatment (if applicable).

Subjects will be randomized in 2:1 ratio to 2 treatment groups (evolocumab and placebo, respectively) in a double-blind manner. The randomization will be stratified by entry statin treatment and hepatitis C status.

Subjects can only be randomized 1 time for this study. The randomization date (study day 1) is to be documented in the subject's medical record and on the enrollment CRF. Randomization numbers will be provided to the site through an IVRS/IWRS.

5.2 **Site Personnel Access to Individual Treatment Assignments**

A subject's treatment assignment should only be unblinded when knowledge of the treatment is essential for the further management of the subject on this study. Unblinding at the study site for any other reason will be considered a protocol deviation.

Refer to the Investigational Product Instruction Manual (IPIM) for a description regarding how responsible pharmacists and investigators will access treatment information via the IVRS/IWRS, in the event that there is a need to break the blind.

The investigator is strongly encouraged to contact the Amgen Clinical Study Manager before unblinding any subject's treatment assignment, but must do so within 1 working day after the event.

6. TREATMENT PROCEDURES

6.1 Classification of Product(s) and/or Medical Device(s)

The Amgen IP used in this study is evolocumab and matching placebo. In several countries, IP is referred to as investigational medicinal product (IMP). In this document, IMP will be referred to as IP.

Protocol Number: 20130286

Date: 30 January 2017

Page 24 of 73

The investigational medical device is the AMD, or the spring based prefilled Al/pen. Note: Ancillary device(s) (ie, any medical device[s] not under study) are described in Section 6.6.

The IPIM, a document external to this protocol, contains detailed information regarding the storage, preparation, destruction, and administration of evolocumab and placebo.

6.2 Investigational Product

Product: Evolocumab

Evolocumab and matching placebo will be manufactured and packaged by Amgen Inc. and distributed using Amgen clinical study drug distribution procedures.

Evolocumab 420 mg and placebo SC will be supplied as an AMD or Al/pen:

- An AMD as a single use, disposable, on-body electro-mechanical injection device that is co-packaged with a prefilled Crystal Zenith cartridge containing 3.5 mL deliverable volume of 120 mg/mL evolocumab or an identical volume of placebo.
- An Al/pen as a single use, disposable, handheld mechanical (spring-based) for fixed dose, SC injection of 140 mg evolocumab in 1.0 mL deliverable volume or an identical volume of placebo.

Placebo will be presented in identical containers and stored/packaged the same as evolocumab.

